1.2 SCHEMA

1.3 SCHEDULE OF ACTIVITIES (SOA)

Procedure	Screening Visit Day -14 to -1	Baseline Visit Week 0/Day 0	DLT Follow up Week 4/Day 28 +/-5 days	Unscheduled Visit	Early Termination Visit
Informed consent	X				
Demographics	X				
Medical History	X				
Physical exam w/vitals	X	X	X	X	X
Performance Status	X	X	X	X	X
Tumor Burden (lesion measurements)	X	X	X	X	X
Concomitant medications review	X	X	X	X	X
Electrocardiogram (ECG)	X		X	X	X
Pathology Report Confirming Diagnosis (specific to lesion marked for injection)	X				
Clinical laboratory samples (safety) ^a	X	X	X	X	X
Pregnancy test	X ^b	X ^c	X ^b	X ^b	X ^b
Blood for Immune Response Evaluation		X	X	X	X
IFx-Hu2.0 dosing		X			
Adverse event review and evaluation		X	X	X	X
Tumor excision for pathological response (final)			X		X

^a **Clinical laboratory samples (safety);** samples will include blood and urine for the following tests:

- Hematology: CBC - hemoglobin, hematocrit, white blood cells (WBC) with differential count, platelet count; blood clotting tests: prothrombin time (PT) and activated partial thromboplastin time (aPTT)
- Biochemistry: CMP - glucose, calcium, albumin, total protein, sodium, potassium, CO2, chloride, BUN, creatinine, total bilirubin, alanine aminotransferase (ALT), aspartate aminotransferase (AST), alkaline phosphatase (ALP), lactate dehydrogenase (LDH), Thyroid tests (TSH and FT4)
- Serology: Hepatitis B Core Antibody (IgM), Hepatitis C Antibody (Anti-HCV), HIV-1/2 Antigen and Antibodies
- Urinalysis: UA with microscopic evaluation
- Anti-double-stranded DNA (anti-dsDNA) antibody test
- Anti-DNase B Titer, Serum

^b **Serum pregnancy test** – indicated only in women of childbearing potential

^c **Urine pregnancy test** done within 24 hours prior to IFx-Hu2.0 administration and results must be available prior to IFx-Hu2.0 administration, – only in women of childbearing potential

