6.1.2 DOSING AND ADMINISTRATION

The amount of drug administered to the participant is 0.1mg injected into a single lesion. IFx-Hu2.0 must be administered within 4 hours of constitution (see Investigator's Brochure section 3.3).

IFx-Hu2.0 is intended for intralesional (i.e. cutaneous, subcutaneous, or lymph nodal) injection. All participants will be monitored for 30 minutes after injection for any immediate adverse events. Participants must abstain from caffeine- or xanthine-containing products (e.g., coffee, tea, cola drinks, and chocolate) for 6 hours and abstain from alcohol for 24 hours before the administration of IFx-Hu2.0.

Administration

1. Avoid placing fingers near the lesion being injected to prevent needlesticks.
2. Use a single insertion point for each lesion.
3. Inject evenly throughout the lesion on multiple tracks, pulling the needle back after injecting a portion of the drug without withdrawing it from the lesion, then rotating it radially on another track until the entire lesion is treated. If the lesion is resistant to drug injection, apply slow, steady pressure, moving the needle slightly as needed. Local anesthetic should not be injected into the lesion or the surrounding tissue, since it may alter pH and therefore drug stability.
4. Withdraw the needle slowly to reduce the risk of drug leakage.
5. Clean the injection site and surrounding area with an alcohol pad.

A single dose (0.1mg) will be used in this trial and at a single timepoint, therefore no dose escalation or reduction is proposed.

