6. Tumor lesion measurement (longest diameter)
7. Urine pregnancy tests for females of reproductive potential; done within 24 hours prior to IFx-Hu2.0 administration, and results must be available prior to IFx-Hu2.0 administration

8. 40 mL of blood for exploratory analysis
9. IFx-Hu2.0 administration

Final Visit (Day 28 ± 5 days) or Early Termination Visit

1. Concomitant medications
2. ECOG performance status
3. Physical exam, including vital signs, weight
4. Electrocardiogram (ECG)
5. Laboratory tests
 - 5.1. Hematology: CBC - hemoglobin, hematocrit, white blood cells (WBC) with differential count, platelet count; blood clotting tests: prothrombin time (PT) and activated partial thromboplastin time (aPTT)
 - 5.2. Biochemistry: CMP - glucose, calcium, albumin, total protein, sodium, potassium, CO2, chloride, BUN, creatinine, total bilirubin, alanine aminotransferase (ALT), aspartate aminotransferase (AST), alkaline phosphatase (ALP), lactate dehydrogenase (LDH), Thyroid tests (TSH and FT4)
 - 5.3. Urinalysis: UA with microscopic evaluation
 - 5.4. Anti-double-stranded DNA (anti-dsDNA) antibody test
 - 5.5. Anti-DNase B Titer, Serum
6. Adverse event recording per CTCAE v5.0
7. Tumor lesion measurement (longest diameter)
8. Serum pregnancy tests for females of reproductive potential
9. 40 mL of blood for immune response evaluation
10. Tumor excision (wide local excision) for pathological response (final)

Unscheduled Visit

If participants require a visit between the baseline and final study visits, then the following procedures may be performed, as indicated (per investigator discretion):

1. Concomitant medications
2. ECOG performance status
3. Physical exam, including vital signs, weight
4. Electrocardiogram (ECG)
5. Laboratory tests
 - 5.1. Hematology: CBC - hemoglobin, hematocrit, white blood cells (WBC) with differential count, platelet count; blood clotting tests: prothrombin time (PT) and activated partial thromboplastin time (aPTT)
 - 5.2. Biochemistry: CMP - glucose, calcium, albumin, total protein, sodium, potassium, CO2, chloride, BUN, creatinine, total bilirubin, alanine aminotransferase (ALT), aspartate aminotransferase (AST), alkaline phosphatase (ALP), lactate dehydrogenase (LDH), Thyroid tests (TSH and FT4)
 - 5.3. Urinalysis: UA with microscopic evaluation
 - 5.4. Anti-double-stranded DNA (anti-dsDNA) antibody test
 - 5.5. Anti-DNase B Titer, Serum
6. Adverse event recording per CTCAE v5.0

7. Tumor lesion measurement (longest diameter)

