8.2.4 TIME PERIOD AND FREQUENCY FOR EVENT ASSESSMENT AND FOLLOW-UP

The occurrence of an adverse event (AE) or serious adverse event (SAE) may come to the attention of study personnel during study visits and interviews of a study participant presenting for medical care, or upon review by a study monitor.

All AEs including local and systemic reactions not meeting the criteria for SAEs will be captured on the appropriate case report form (CRF). Information to be collected includes event description, time of onset, clinician's assessment of severity, relationship to study product (assessed only by those with the training and authority to make a diagnosis), and time of resolution/stabilization of the event. All AEs occurring while on study must be documented appropriately regardless of relationship.

Any medical condition that is present at the time that the participant is screened will be considered as baseline and not reported as an AE. However, if the a pre-existing condition deteriorates at any time during the study, it will be recorded as an AE, with use of descriptors in the AE term to designate that it is a pre-existing condition (e.g., worsening of or exacerbation of)

Changes in the severity of an AE will be documented to allow an assessment of the duration of the event at each level of severity to be performed.

The investigator will record all reportable events with start dates occurring any time after informed consent is obtained until 7 (for non-serious AEs) or 30 days (for SAEs) after the last day of study participation. At each study visit, the investigator will inquire about the occurrence of AE/SAEs since the last visit. Events will be followed for outcome information until resolution or stabilization.

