3. STATISTICAL METHODS

3.1 *General*

All data will be analyzed using the Statistical Analysis System (SAS®; Version 9.2 or higher). Continuous variables will be summarized using descriptive statistics, including sample size, mean, standard deviation (SD), median, minimum, and maximum. Categorical variables will be summarized using number and percent of subjects for each outcome.

All statistical tests will be two sided, and statistical significance level is 0.05.

3.2 *Subject Disposition, Demographics and Baseline Characters*

- Reasons for withdrawal will be summarized.
- Demographics and baseline characters will be summarized on safety analysis set using descriptive statistics.
- Medical history will be summarized with MedDRA system organ class (SOC) and preferred term (PT) for Safety analysis set.
- Prior and concomitant medications will be summarized with WHO Drug Class 3 name for Analysis of Study Endpoints

3.2.1 *Safety Analysis*

The safety analysis will be conducted on safety analysis set that includes all treated subjects.

Safety endpoints will be analyzed as summary statistics during treatment and/or as change scores from baselines such as shift tables. Treatment emergent adverse events (TEAEs) will be coded using Medical Dictionary for Regulatory Activities (MedDRA). TEAE severity and relationship to study treatment will be presented by dose cohort, MedDRA system organ class (SOC) and preferred term (PT).

The information reported about each AE will be the start date, stop date, severity, relationship, outcome, and duration). AEs leading to premature discontinuation from the study and serious treatment emergent AEs will be presented with either a summary table or a data listing.

- **Adverse Events**

TEAEs are defined as signs or symptoms that emerge during treatment or within 28 days of the last dose of Investigational Product, including those signs and symptoms that have been absent pre-treatment or that have worsened relative to the pre-treatment assessment. Any adverse event considered related to treatment will also be considered a TEAE, regardless of the elapsed time since the last dose of Investigational Product.

Number and percentage of subject with any DLT will be reported by dose cohort, MedDRA SOC and PT. Overall DLT rate for safety analysis set will be provided with 95%CI.

Number and percentage of subject with any TEAEs will be summarized by MedDRA SOC, PT, intensity, and relationship to the study treatment.

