4.5.6. Listings of safety data

Listing 16.2.7.1 Treatment Emergent Adverse Events - Safety Analysis Set

Listing 16.2.7.2 Serious Treatment Emergent Adverse Events - Safety Analysis Set

Listing 16.2.7.3 Treatment Emergent Adverse Events of DLT – Safety Analysis Set

Listing 16.2.7.4 Study Treatment Related Adverse Events – Safety Analysis Set

- Listing 16.2.7.5 Immune Response Treatment Emergent Adverse Events – Safety Analysis Set
- Listing 16.2.7.6 Treatment Emergent Adverse Events Leading to Study Discontinuation - Safety Analysis Set
- Listing 16.2.8.1 Chemistry Laboratory Tests - Safety Analysis Set
- Listing 16.2.8.2 Hematology Laboratory Tests - Safety Analysis Set
- Listing 16.2.8.3 Urinalysis Laboratory Tests - Safety Analysis Set
- Listing 16.2.8.4 Pregnancy Tests - Safety Analysis Set
- Listing 16.2.9.1 Vital Signs - Safety Analysis Set
- Listing 16.2.9.2 12-Lead Electrocardiograms - Safety Analysis Set
- Listing 16.2.9.3 ECOG Performance Status - Safety Analysis Set
- Listing 16.2.9.4 Physical Examinations - Safety Analysis Set
- Listing 16.2.10.1 Pathological Response Results - Safety Analysis Set

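### The 28-day TEAE limit leaves unrelated SAEs and deaths starting after Day 28 without an assured output, and it cuts across the period after excision

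*SAP*

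**What the plan says.** **Analysis window.** SAP section 3.2.1: "TEAEs are defined as signs or symptoms that emerge during treatment or within 28 days of the last dose of Investigational Product". The same paragraph adds an exception without a time limit: "Any adverse event considered related to treatment will also be considered a TEAE, regardless of the elapsed time since the last dose".

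**Dosing.** Protocol section 6.1.2: "A single dose (0.1mg) will be used in this trial and at a single timepoint". The last dose is therefore the only dose, on Day 0.

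**Collection window.** Protocol section 8.2.4 has the investigator record events "until 7 (for non-serious AEs) or 30 days (for SAEs) after the last day of study participation".

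**Final visit and surgery.** The Schedule of Activities heads the only scheduled visit after dosing "DLT Follow up Week 4/Day 28 +/-5 days". Protocol section 6.1.3 heads it "Final Visit (Day 28 ± 5 days) or Early Termination Visit" and lists, as its last procedure, "Tumor excision (wide local excision) for pathological response (final". The schedule also places the excision at an early termination visit.

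**Outputs.** SAP section 4.5.6 plans "Listing 16.2.7.2 Serious Treatment Emergent Adverse Events - Safety Analysis Set". The serious-event table (14.3.1.4), the tables by SOC and PT (14.3.1.2, 14.3.1.7), the general AE listing (16.2.7.1) and the discontinuation listing (16.2.7.6) carry the same restriction. No death table and no listing of all SAEs is planned.

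**The concern.** Safety is a primary endpoint, and the TEAE tables and listings are its main report. The protocol asks sites to collect events that the SAP's definition then excludes, and two things follow.

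First, an SAE or death that starts after Day 28 and is judged unrelated is recorded, but no planned serious-event output is bound to show it. Whether a late serious event is reported then rests on a relatedness judgement in an open-label trial.

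Second, the only scheduled visit after dosing is also the day of surgery, so the Day 28 limit runs through the post-operative period. The same unrelated wound event can be counted in one patient and left out in another because their visits fell on different days. Events that are counted are pooled with those that arose before surgery, which blurs the picture of the drug itself.

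**Working it through.** **Inputs**
- Dose on Day 0 (protocol 6.1.2).
- Final visit on Day 28 ± 5, so Day 23 to 33, which is 11 allowed days (protocol 1.3 and 6.1.3).
- Collection to 7 days (non-serious) or 30 days (SAE) after the last day of participation (protocol 8.2.4). I take that last day to be the final visit.
- TEAE limit for unrelated events: onset by Day 28 (SAP 3.2.1).

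**The plan's own timeline.** Screening of up to 14 days plus 28 days gives 14 + 28 = 42 days, or 6.0 weeks. This matches the approximate six weeks stated in protocol 6.1.3. With the 5-day allowance it is 47 days, or 6.7 weeks. The Day 0 to Day 33 reading of the schedule is therefore sound.

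**End of collection = final visit day + 7 or + 30**

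| Final visit | Non-serious collection ends | Days past Day 28 | SAE collection ends | Days past Day 28 |
|---|---|---|---|---|
| Day 23 | 23 + 7 = Day 30 | 2 | 23 + 30 = Day 53 | 25 |
| Day 28 | 28 + 7 = Day 35 | 7 | 28 + 30 = Day 58 | 30 |
| Day 33 | 33 + 7 = Day 40 | 12 | 33 + 30 = Day 63 | 35 |

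**Unrelated events after excision.** For surgery on day s, the onset days inside the TEAE window run from s to 28. Their number is 28 − s + 1 if s is 28 or less, and 0 otherwise. Collection covers 8 onset days for non-serious events (s to s + 7) and 31 for SAEs (s to s + 30).

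| Surgery day | 23 | 24 | 25 | 26 | 27 | 28 | 29 to 33 |
|---|---|---|---|---|---|---|---|
| Onset days inside the window | 6 | 5 | 4 | 3 | 2 | 1 | 0 |

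Five of the 11 allowed visit days (29 to 33) leave none. As an example, take an unrelated wound event that starts two days after surgery. Surgery on Day 26 gives onset on Day 28, which is counted. Surgery on Day 27 gives onset on Day 29, which is not.

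**Where could an unrelated SAE with onset after Day 28 appear?**
- Table 14.3.1.4 and Listings 16.2.7.1, 16.2.7.2 and 16.2.7.6: no, all are limited to TEAEs.
- Listing 16.2.7.4: its title is not limited to TEAEs, but it covers related events only.
- Table 14.3.1.1, the overall AE summary: possibly. Its title is not limited to TEAEs. The SAP says its templates are in an appendix, which is not in the text available here. It is a summary table, not a patient-level listing.
- Table 14.1.1.1 and Listing 16.2.1.1 (disposition): possibly, for a death that ended participation. The 30-day SAE period starts after the last day of participation, when a patient who attended the final visit already counts as a completer (protocol 4.3). A later death is not sure to appear there.

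**The case against.** A 28-day window is a reasonable choice in itself. It matches the 4-week DLT period and the nominal final visit, and the SAP keeps related events in without a time limit. Relatedness is not left unchecked: protocol 8.2.3.2 says the product must always be under suspicion, and section 8.2.5 has the medical monitor assess it too. No visit is scheduled after the final visit, so late events may be few. All of this stands, and it is why the window itself need not change. It does not supply an output for serious events that the protocol requires sites to record.

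A reader might infer three stronger things that the documents do not support.

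- **That late unrelated SAEs and deaths appear in no output at all.** Table 14.3.1.1 or the disposition outputs might show some. What can be said is that no table or listing is assured.
- **That excision events count only when surgery falls on Day 23 to 28.** The test is the day of onset, not of surgery. Surgery on Day 27 with unrelated onset on Day 30 is excluded. An excision at early termination before Day 23 can produce counted events. A related event counts whatever the day.
- **That the primary DLT or feasibility result is affected.** A DLT must be possibly related or more and fall within 4 weeks of dosing (SAP 2.2.1 and 3.7), so a limit on unrelated events after Day 28 cannot change it. Whether a grade 3 wound event at the injected site before then is called possibly related is a question of attribution, separate from the window.

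The gap of 25 to 35 days is also a count of calendar days, not of events. The documents give no rate for wound events or late SAEs, so the number of events involved cannot be estimated.

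**Conclusion.** The mismatch is real and should be fixed, as a gap in safety reporting. Unrelated non-serious events are collected for 2 to 12 days, and unrelated SAEs for 25 to 35 days, beyond the TEAE limit, and the serious ones have no assured table or listing. The reported rate of unrelated surgical events depends partly on scheduling, with 6 down to 0 countable onset days as surgery moves from Day 23 to Day 29 or later, and those counted are mixed with events from before surgery.

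This rests on three readings: that the window closes at the end of Day 28, that the last day of participation is the final visit, and that patients attend between Day 23 and Day 33. An early termination visit before Day 23 brings the end of collection forward by the same number of days. If the template for Table 14.3.1.1 covers all adverse events regardless of TEAE status, late events would be counted there, but a patient-level listing would still be missing.

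**What to change.** 1. Add to the SAP a listing and a count of all SAEs and all deaths through the end of collection in protocol section 8.2.4, regardless of TEAE status, with day of onset and relatedness shown.
2. Derive a flag for each adverse event: onset before or after the excision. For events on the day of surgery, use the time of onset, which protocol 8.2.4 already collects. If the clock time of surgery is not recorded, state a default for same-day events.
3. Present the TEAE summary split by this flag, with the pre-excision part as the clearer view of the drug. Keep related events in on either side.

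Lengthening the TEAE window to match collection is optional and not needed once these are in place. It would draw in more surgical events and give one definition two end dates, up to Day 40 for non-serious events and up to Day 63 for SAEs.

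The cost is SAP wording, one listing, one derived flag and slightly longer tables. No visit, procedure or treatment changes.

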3.3.2. Exploratory Analyses

Patient samples (plasma and/or serum) will be assayed to detect tumor antigen specific antibody generation in addition to a protein biomarker discovery assay specific to immuno-oncology therapy assessments.

3.3.3. Subgroup Analyses

No subgroup analyses of safety endpoints will be planned.

3.4. Handling of Missing Data

Missing data will not be imputed for safety analyses.

3.5. Protocol Deviations

Listing for all protocol deviations will be provided.

3.6. Interim Analyses

Interim analysis will not be planned.

3.7. Key Data Items

Study Analysis Population Definition:

- Safety analysis set: All enrolled patients who have received at least 1 dose of IFx-Hu2.0.

Important Derived Variables:

- Age = (Screening Date – Date of Birth +1)/365.25.
- Prior Medications and Treatments: the medications and treatments started before enrolled to the study.
- Concomitant Medication and Treatments: the medications and treatments started after being enrolled to the study.
- Baseline: Day 0 (Baseline Visit). All clinical measurements collected at Day 0 or before the dose of IFx-Hu2.0 on Day 0 will be analyzed as baseline.
- Post Baseline (post dose): All clinical measurements collected after the dose of IFx-Hu2.0 on Day 0 will be analyzed as post baseline.
- Dose-Limiting Toxicity (DLT): Treatment emergent adverse event (TEAE) equal to or greater than grade 3, at least possibly related to the investigational agent, occurring within a 4-week period following IFx-Hu2.0 administration

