6.4 CONCOMITANT THERAPY

For this protocol, a prescription medication is defined as a medication that can be prescribed only by a properly authorized/licensed clinician. Medications to be reported in the Case Report Form (CRF) are concomitant prescription medications, over-the-counter medications, and supplements taken during participation and over 90 days prior to enrollment.

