4. OUTPUT PLANNED FOR THE STUDY REPORT

4.3. Tables to be Included in Study Report

In the following sections, the different results are presented in the order in which it is planned to make them appear in the study report.

The table templates are available in the Appendix of the SAP. The content shown in the templates is only meant as an example. It is not based on real study data or details concerning design.

4.3.2. *Summary of Subject Information*

Table 14.1.1.1 Subject Disposition – Safety Analysis Set

4.3.3. *Demographic and Other Baseline Characteristics*

Table 14.1.2.1 Summary of Demographics – Safety analysis set

Table 14.1.2.2 Number (%) of Subjects with Medical History by MedDRA System Organ Class and Preferred Term - Safety Analysis Set

Table 14.1.2.3 Number (%) of Subjects with Current Medical Conditions by MedDRA System Organ Class and Preferred Term - Safety Analysis Set

Table 14.1.2.4 Number (%) of Subjects with Prior Medications by WHO Drug Class 3 Name and Preferred Term - Safety Analysis Set

Table 14.1.2.5 Number (%) of Subjects with Concomitant Medications by WHO Drug Class 3 Name and Preferred Term - Safety Analysis Set

4.3.4. *Summary of Safety Endpoints*

Table 14.3.1.1 Overall Summary of Adverse Events - Safety Analysis Set

Table 14.3.1.2 Number (%) of Subjects with TEAEs by SOC and PT - Safety Analysis Set

Table 14.3.1.3 Number (%) of Subjects with DLT by MedDRA SOC and PT – Safety Analysis Set

Table 14.3.1.4 Number (%) of Subjects with Serious TEAE by MedDRA SOC and PT – Safety Analysis Set

Table 14.3.1.5 Number (%) of Subjects with Study Treatment Related TEAE by MedDRA SOC and PT – Safety Analysis Set

Table 14.3.1.6 Number (%) of Subjects with Immune Response Treatment Emergent Adverse Events – Safety Analysis Set

Table 14.3.1.7 Number (%) of Subjects with TEAE by MedDRA Preferred Term and Overall Frequency – Safety Analysis Set

Table 14.3.2.1 Summary of Chemistry Laboratory Tests by Visit - Safety Analysis Set

Table 14.3.2.2 Summary of Hematology Laboratory Tests by Visit - Safety Analysis Set

Table 14.3.2.3 Summary of Urinalysis Laboratory Tests by Visit - Safety Analysis Set

Table 14.3.2.4 Summary of Qualitative Urinalysis Laboratory Tests by Visit - Safety Analysis Set

Table 14.3.2.5 Shift Tables of Laboratory Results from Baseline to the Worst Post-Baseline Visit (Chemistry) - Safety Analysis Set

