4.5.3. Demographics and Baseline Characters

Listing 16.2.4.1 Demographic and Baseline Characteristics - Safety Analysis Set

Listing 16.2.4.2 Subjects with Past and Current Medical Conditions - Safety Analysis Set

Listing 16.2.4.3 Subjects with Prior Medications - Safety Analysis Set

Listing 16.2.4.4 Subjects with Concomitant Medications - Safety Analysis Set

Listing 16.2.4.5 Subjects with Disease Characteristics for Primary Tumor Type – Safety Analysis Set

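### SAP 3.7 sorts medications by start date alone, so a drug begun before enrolment and still in use after the dose is counted only as prior

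*SAP*

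**What the plan says.** SAP 3.7 (Key Data Items) gives two definitions that matter here:

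- For drugs that count as in use during the trial, the wording is "Concomitant Medication and Treatments: the medications and treatments started after being enrolled to the study".
- For drugs that count as earlier treatment, the wording is "Prior Medications and Treatments: the medications and treatments started before enrolled to the study".

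Each uses one date, the start, compared with enrolment. Stop date and ongoing status appear in neither.

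The only other SAP text on handling medications is in SAP 3.2: "Prior and concomitant medications will be summarized with WHO Drug Class 3 name". It sets the coding level. The outputs are Table 14.1.2.4 and Listing 16.2.4.3 for prior use, and for concomitant use Table 14.1.2.5 ("Number (%) of Subjects with Concomitant Medications by WHO Drug Class 3 Name and Preferred Term") and "Listing 16.2.4.4 Subjects with Concomitant Medications - Safety Analysis Set".

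Protocol 6.4 sets what the CRF collects. The medications to be recorded "are concomitant prescription medications, over-the-counter medications, and supplements taken during participation and over 90 days prior to enrollment". The Schedule of Activities (Protocol 1.3) has a concomitant medication review at every visit, including Screening.

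**The concern.** A concomitant medication table in a single-arm safety report should tell the reader what participants were taking while adverse events were being collected. Under SAP 3.7 it tells the reader only what they began after enrolment. Long-term treatment that was already established and simply continued is left out.

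Such users are foreseeable. Protocol 5.1 accommodates anticoagulant therapy in its clotting criteria. Protocol 5.2 excludes systemic corticosteroid only above a stated prednisone level and does not exclude medication for reactive airway disease. In the earlier IFx-Hu2.0 monotherapy trial, Table 2 of Protocol 2.3.1 reports treatment-related tumor hemorrhage in 2 patients (n=6). A reader who sees bleeding events in this trial and turns to Table 14.1.2.5 for anticoagulant use would miss everyone who was on the drug before enrolment, unless they had also started another one afterwards.

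**Working it through.** The plan gives no figure to reproduce and no formula applies. The check is to apply the two definitions literally to each start and stop pattern, and then to look for any text that changes the result.

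| Pattern | Class under SAP 3.7 | In use on or after the dose? |
|---|---|---|
| (a) Begun and stopped before enrolment | Prior | No |
| (b) Begun before enrolment, still taken on or after the dose | Prior only | Yes |
| (c) Begun after enrolment, stopped before the dose | Concomitant | No |
| (d) Begun after enrolment, taken on or after the dose | Concomitant | Yes |
| (e) Begun on the day of enrolment | Not clearly covered by either | Depends |

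**Pattern (b)** is the main problem. The drug is in use during follow-up but absent from Table 14.1.2.5 and Listing 16.2.4.4. In Table 14.1.2.4 it is pooled with pattern (a), so stopped and continuing drugs are not told apart by definition.

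**Patterns (c) and (e)** are secondary. They depend on which date counts as enrolment, and the text supplied does not define it. If enrolment is dated to Day 0, at dosing, pattern (c) cannot occur.

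**Is there an override?** None is visible. SAP 3.2 gives the coding level. SAP 3.8 declares no change from the protocol's planned analysis. SAP 4.3.3 separates medical history from current conditions (Tables 14.1.2.2 and 14.1.2.3), but the SAP draws no such line for drugs.

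**Which time anchor does the SAP use elsewhere?** Measurements are split at the dose: "All clinical measurements collected after the dose of IFx-Hu2.0 on Day 0 will be analyzed as post baseline". Adverse events are also tied to dosing: "TEAEs are defined as signs or symptoms that emerge during treatment or within 28 days of the last dose of Investigational Product". The medication split is tied to enrolment, so the concomitant table does not cover the same period as the adverse event tables beside which it would be read.

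**Size.** For a given drug class, pattern (b) lowers the count in Table 14.1.2.5 by the number of participants whose only use of that class on or after the dose is a drug begun before enrolment. Neither document gives a rate of medication use, so that number cannot be computed.

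**The case against.** Four points can fairly be made against this.

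1. **Nothing is lost.** A reader might infer that continuing drugs vanish from the report. They do not: every pattern (b) drug is in Table 14.1.2.4 and Listing 16.2.4.3. A reader might also infer that DLT attribution is affected. It is not, because Protocol 8.2.3.2 has relatedness judged by the investigator who examines the participant, and no planned analysis uses Table 14.1.2.5. This stands, and it limits the point to labelling.

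2. **The protocol does not define concomitant by use.** It is tempting to say that SAP 3.7 contradicts Protocol 6.4. But 6.4 is a collection rule for the CRF. Its scope also reaches back 90 days before enrolment, and it refers to enrolment just as the SAP does. The visit-schedule entries are procedure labels. A contradiction is not supported. What 6.4 does show is that continuing drugs are meant to be recorded.

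3. **An enrolment anchor is not in itself an error.** Tying adverse events to dosing does not oblige the SAP to do the same for medications, and ongoing use could be added while keeping enrolment as the cut. This stands. The fault is the missing condition on continuing use.

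4. **Some text is unseen or damaged.** The table templates in the SAP Appendix were not available, so an ongoing flag or stop date in the outputs cannot be ruled out. The SAP 3.2 bullet runs into what looks like a heading, so its ending may be lost. This limits what can be said about the final layout. However, SAP 4.3 calls the template content an example only, and a flag in the prior table would not put the drug into the concomitant table.

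**Conclusion.** The point holds as a minor misclassification in descriptive safety outputs. The SAP 3.7 definitions, read literally, count a drug begun before enrolment and continued past the dose only as prior. Table 14.1.2.5 and Listing 16.2.4.4 then under-report medications in use during follow-up, and Table 14.1.2.4 mixes stopped with continuing drugs. The size is unknown because no usage rate is given. The DLT rate, the feasibility criterion and the stopping boundary are untouched.

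This rests on two assumptions: that the definitions will be programmed as written, and that neither the templates nor any lost text in SAP 3.2 adds a rule for ongoing drugs.

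**What to change.** Reword the two definitions in SAP 3.7:

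- **Concomitant:** any medication or treatment taken on or after the IFx-Hu2.0 dose, whatever its start date.
- **Prior:** any medication or treatment begun before the dose. Those ongoing at the dose are counted in both classes and flagged as ongoing.

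Apply this to Tables 14.1.2.4 and 14.1.2.5 and Listings 16.2.4.3 and 16.2.4.4. The essential change is to include ongoing use. Anchoring on the dose is a convenience that avoids the undefined enrolment date. If the sponsor prefers to keep enrolment as the cut, its date should be defined and the ongoing condition still added.

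Any convention for a missing stop date should be written as a classification rule and reconciled with SAP 3.4, which rules out imputation for safety analyses.

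The cost is a small amount of programming across two tables and two listings. The CRF must also hold a stop date or ongoing status, and neither document says that it does. If it does not, the medication reviews already scheduled at Baseline and Week 4 could record it. No endpoint analysis changes.
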